## 4 Study Procedures

### 4.1 Baseline Assessments

- Participant consented
- Abstracted from chart
  - Age
  - Duration of DM
  - DM medications including use of insulin
  - Fasting glucose, HbA1c, HOMA1-IR, HOMA2-IR, creatinine, testosterone
  - BMI
- Objective assessments
  - Penile length – pubic symphysis to glanular corona
- Subjective questionnaires
  - Disease specific history
  - IIEF-15
- Device usage diary provided for treatment group

### 4.2 3 Month Visit

- Penile length assessment
- Questionnaires
  - 3 month
  - IIEF-15
- Device usage diary retrieved from treatment group
- Device usage diary given to all participants

### 4.3 6 Month Visit

- Penile length assessment
- Questionnaires
- **month**
  - IIEF-15
- Retrieve device usage diary

#### 4.4 Assessment of Length

Penile length measurements will be obtained by a member of the clinical team using a measurement from the pubic symphysis to the corona of the glans penis. Measurements will be obtained at baseline and at the 3 and 6 month follow-ups.

See **Attachments – Device Usage Diary, Disease Specific History, IIEF-15, Questionnaire 3 Month and 6 Month**

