## Study Summary

Title	Penile Length Restoration in Men with Diabetes Mellitus, Type II
IRB Protocol Number	18-006696
Methodology	Controlled randomized study
Overall Study Duration	3 years
Subject Participation Duration	6 months
Objectives	Evaluate the efficacy of the RestoreX penile traction device in restoring length loss secondary to diabetes mellitus
Number of Subjects	120
Diagnosis and Main Inclusion Criteria	Men with diabetes mellitus, type II
Study Device	RestoreX®, penile traction therapy
Duration of Exposure	Subjects in Groups 1-3 will use device for 3 months for 30 minutes, twice daily. Subjects in Group 4 will be control and will not use the device.  After the randomized period, subjects using the device will switch to not using the device (Group 1), using the device once weekly x 30 minutes (Group 2), or continuing to use the device twice daily x 3 months (Group 3).
Reference therapy	The use of the device will be compared against a control group using no traction therapy. Individuals will also be compared to themselves to evaluate changes from baseline.
Statistical Methodology	Stratification of subjects prior to randomization to assure an equal representation based on baseline penile length. Statistical comparisons will be made comparing total penile length prior to and following therapy. Comparisons of subjective questionnaire responses will also be made between groups and at the various time points captured.

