## 2 Study Objectives

### 2.1 Primary Objective

1. The primary objective is to assess penile length pre and post completion of RestoreX® traction therapy compared to control groups (no treatment) of DM subjects.

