### 3.5 Study Schema

All patients will have been previously seen at Mayo Clinic for a condition of DM. Following enrollment, key factors relating to their underlying condition will be abstracted from the chart by a study coordinator, including age, duration of disease (if known), number of DM medications, use of insulin, most recent fasting glucose and HbA1c, creatinine, and testosterone, HOMA1-IR, HOMA2-IR, and BMI. If any of these variables are not available, no additional attempts will be made to retrieve the information.

At the initial appointment, patients will also undergo a penile length assessment by a urology provider and Men's Health Nurse and receive questionnaires (IIEF-15 and disease specific history)

Once consent and study assessments are completed, the patients will be randomized into one of four groups:

1. PTT for 30 min 2x/day x 3 months, followed by no treatment x 3 months
2. PTT for 30 min 2x/day x 3 months, followed by once weekly (30 minutes) x 3 months
3. PTT for 30 min 2x/day x 6 months
4. Control (no treatment)

Patients in the treatment arm will record a daily journal of their usage of the device. Patients will then begin using the device as instructed for the times appropriate to their group.

After 3 months of using the device (+1.5 months permitted), patients will return for subsequent assessments (see below) and a follow-up questionnaire. At this time, patients will be encouraged to report any adverse events. They will also be requested to bring their device back to the clinic to review proper usage and any questions on the device. After completion of the subsequent assessments, patients will begin the second phase of the trial.

After 6 months (+ 1.5 months permitted) patients will return to the clinic to undergo final assessments, which are identical to the 3-month assessments.

Since participants are being asked to travel to Mayo Clinic for subsequent assessments, we will provide a remuneration amount of up to \$600. The purpose is to assist participants in their travel to and from Mayo Clinic. Those that provide consent will be provided \$100 after their baseline assessment. After their second and third visits (3 and 6-months, respectively), they will receive \$250 for a possible total of \$600.

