### **3.6 Randomization Protocol**

Following enrollment and completion of the initial length assessment, patients will be categorized into the appropriate strata based on their baseline stretched penile length; strata categorized as <10 cm, 10cm-13cm, 13.1cm-16cm, >16cm stretched length. Each stratum will have a separate randomization table provided such that one of three possible outcomes will occur no less frequently than every other case. This is done to better account for baseline variables that may impact outcomes and to assist with matching groupings appropriately.

The explanation of which grouping the patient is assigned will then be reviewed, and if the patient subject is assigned to the treatment group, a RestoreX® device will be provided.

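### The primary length measure is named three ways and nothing holds reader or technique constant across visits; the cost is precision against control, and possible bias in the within-man and historical comparisons

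*Combined protocol and SAP*

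**What the plan says.** Penile length is the primary outcome. Section 2.1 sets out to "assess penile length pre and post completion of RestoreX® traction therapy compared to control groups (no treatment) of DM subjects" and gives neither landmarks nor state.

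Elsewhere the measure is named as follows:

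- **Study Summary:** "Statistical comparisons will be made comparing total penile length prior to and following therapy".
- **Section 4.1 (baseline):** "Penile length – pubic symphysis to glanular corona".
- **Section 4.4 (all visits):** readings are "obtained by a member of the clinical team using a measurement from the pubic symphysis to the corona of the glans penis", and "Measurements will be obtained at baseline and at the 3 and 6 month follow-ups".
- **Section 3.6 (randomisation):** men are "categorized into the appropriate strata based on their baseline stretched penile length".
- **Section 5.2 (analysis):** stretched length at baseline defines the men to be compared with each other, and is also what all data are normalised by.
- **Sections 4.2 and 4.3 (follow-up):** a length assessment is listed without description.

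On who measures, section 3.5 says that at the initial appointment "patients will also undergo a penile length assessment by a urology provider and Men's Health Nurse". It makes the 6-month assessments the same as the 3-month ones, but does not tie either to baseline. Section 4.4 leaves the reader open within the clinical team. The attachments were not available for this review; none of those listed in 4.4 is named as a procedure for measuring length.

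**The concern.** A length to the corona leaves out the glans, so the *total* length in the Study Summary is not what section 4 collects. Sections 4.1 and 4.4 give the landmarks but not the state, whereas 3.6 and 5.2 give the state but not the landmarks. A reader has to combine the sections to reach stretched length from symphysis to corona, and has to assume that it also applies at follow-up.

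A stretched reading depends on how hard the examiner pulls. If one person reads a man at baseline and another at month 3, the difference between their techniques goes straight into his change score. Section 5.2 then uses such readings in three ways: traction against no traction, baseline against post-traction within men, and together with historical records. Randomisation protects only the first. The baseline reading also serves as the normalising quantity, so its error carries into every normalised result.

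**Working it through.** **Plan's own figures.** The protocol gives 4 × 30 = 120 men, but no SD, effect size, alpha or power. No stated figure depends on this point, so every SD below is an assumption.

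**Step 1: measurement error in one man's change score.** Assume a within-reader SD sw = 0.5 cm and a between-reader SD sb of 0.3, 0.7 or 1.0 cm, with independent errors. A reader's own bias cancels if he or she reads both visits.

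- Same reader, one reading per visit: √(2·sw²) = √(2 × 0.25) = 0.71 cm.
- Different readers, one reading per visit: √(2·sw² + 2·sb²).
- Same reader, mean of two readings: √(2·sw²/2) = √0.25 = 0.50 cm.
- Different readers, mean of two readings: √(2·sw²/2 + 2·sb²).

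| sb (cm) | Different readers, one reading | Different readers, mean of two |
|---|---|---|
| 0.3 | √(0.50 + 0.18) = 0.82 | √(0.25 + 0.18) = 0.66 |
| 0.7 | √(0.50 + 0.98) = 1.22 | √(0.25 + 0.98) = 1.11 |
| 1.0 | √(0.50 + 2.00) = 1.58 | √(0.25 + 2.00) = 1.50 |

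Averaging does nothing about sb. At sb of 0.7 or 1.0 cm, keeping the same reader is worth more than a second reading. The 0.50 cm needs independent errors: if the second reading merely repeats the first, the SD stays at 0.71 cm.

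**Step 2: randomised comparison, shift common to all arms.** If follow-up readings differ from baseline by b in every arm, the contrast is (traction change + b) − (control change + b), and b drops out. Simulation with 90 against 30 men, no true effect and SD of change 1 gave rejection rates of 0.061, 0.051 and 0.052 for b = 0, 0.5 and 1 SD. There is no upward trend, and the highest value is the one with no shift.

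**Step 3: randomised comparison, random inconsistency.** Let it add a component with SD e, in units of the SD of change without it, so that the SD becomes √(1 + e²). Assume two-sided alpha 0.05 and 80% power at e = 0. The detectable effect is then 2.80 × √(1/30 + 1/30) = 0.72 SD for 30 against 30, or 2.80 × √(1/90 + 1/30) = 0.59 SD for 90 against 30. In both cases power at that effect is about Φ(2.80/√(1 + e²) − 1.96):

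| e | 0 | 0.25 | 0.5 | 0.75 | 1.0 |
|---|---|---|---|---|---|
| Power | 80% | 78% | 71% | 61% | 51% |

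The centimetre figures in Step 1 cannot be converted to e, because the protocol gives no SD of change.

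**Step 4: within-man comparison.** Here b does not cancel. In the same simulation, a one-sample test in 30 men with no true effect rejected in about 5% of runs at b = 0, 76% at 0.5 SD and 100% at 1 SD. Historical readings have the same weakness, since nothing ties their technique to the trial's.

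**The case against.** Much can be said for the plan. Sections 4.1 and 4.4 agree on the landmarks, and 4.4 applies them at all three visits. *Total* occurs once as a description of the measure, in a summary. Section 3.6 assigns strata after the initial length assessment, so the natural reading is that the 4.1 measurement is the stretched one. That stands: on landmark and state, this is a matter of aligning the wording.

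Several stronger readings are tempting, and the documents do not support them.

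- *Different people measure at baseline and follow-up.* Section 4.4 covers baseline too, and the two roles in 3.5 can both belong to the clinical team. The reader is left open; no switch is described.
- *Two baseline values have to be combined.* Section 3.5 speaks of one assessment by two staff, which fits a joint reading.
- *Men will be put in the wrong stratum.* That needs landmarks or states to be mixed in practice, and section 4 describes only one landmark. Misplacement would not in itself bias a randomised comparison.
- *Measurement differences will swamp the effect.* The protocol states no effect size or SD to compare them with.

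It is also fair that only change scores with a change of reader carry the between-reader term, and that Step 1 leaves out true variation between men, so total SD would rise by a smaller proportion than those figures suggest. What survives is that nothing keeps reader or technique constant, and that 5.2 plans two comparisons that randomisation does not protect.

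**Conclusion.** The point holds in limited form. The primary measure needs one definition, and 4.4 permits changes of reader that could be largely avoided at little cost. On the assumed SDs, a change of reader raises the measurement-error SD of a man's change score from 0.71 cm to between 0.82 and 1.58 cm; the same reader averaging two independent readings lowers it to 0.50 cm.

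For traction against control, the consequence is lost precision in proportion to how often readers change. A reader might infer that the randomised effect estimate is biased. That would require measurement that differs by arm. The protocol does not state that the reader is blinded, so this cannot be ruled out, but nothing in the text shows it. Bias is a direct risk for the within-man comparison and for the historical records. The case for acting rests on the low cost of the remedy, not on a demonstrated failure of the primary comparison.

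**What to change.** - In 4.4, state one measure for strata, baseline, month 3 and month 6: stretched length, pubic symphysis to corona. Change *total* in the Study Summary to match, and use the same term in 2.1, 3.6, 4.1 and 5.2.
- Have the same reader measure a given man at all three visits where possible. Since 3.5 names two roles at the first visit, say which one is the reader of record.
- Take two readings per visit and analyse their mean.
- Record the reader's role code on the form at each visit.

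The cost is protocol wording, some scheduling effort to keep readers matched to men, and about one minute per visit. No more men are needed. Section 3.5 places its two roles only at the initial appointment, so their availability at months 3 and 6 should be confirmed.

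### Section 4.4 sets no condition on time since the last traction session before length is read, so any temporary stretch would be counted only in groups using the device

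*Combined protocol and SAP*

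**What the plan says.** Section 4.4 contains the whole measurement method: "Penile length measurements will be obtained by a member of the clinical team using a measurement from the pubic symphysis to the corona", followed by "Measurements will be obtained at baseline and at the 3 and 6 month follow-ups". The visit lists in 4.1 to 4.3 and the schedule in 4.5 add which assessments are done, but nothing on timing relative to device use.

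Section 3.5 gives the regimens. Group 1 has "PTT for 30 min 2x/day x 3 months, followed by no treatment x 3 months". Group 2 has the same first three months and then one session a week. Group 3 has "PTT for 30 min 2x/day x 6 months". Group 4 is untreated. On the first follow-up visit, 3.5 says "After 3 months of using the device (+1.5 months permitted), patients will return for subsequent assessments", with the same tolerance at month 6. It starts the second phase only once the month-3 assessments are done. Of that visit it also says "They will also be requested to bring their device back to the clinic to review proper usage and any questions on the device", without stating whether length is read before or after this review.

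The primary objective (2.1) is to "assess penile length pre and post completion of RestoreX® traction therapy compared to control groups (no treatment) of DM subjects". The Study Summary states the aim as "Evaluate the efficacy of the RestoreX penile traction device in restoring length loss secondary to diabetes mellitus". Men on traction keep a daily usage journal (3.5), but no analysis in 5.2 uses the time since the last session.

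**The concern.** Men assigned to traction can use the device at home or while travelling on the day they are measured. If a session leaves the tissue temporarily longer, the reading would combine that after-effect with lasting change. Controls cannot have it. Baseline readings cannot have it from trial use, because the device is supplied only after the baseline reading and randomisation (3.6). Neither change from baseline nor normalisation by baseline length (5.2) would therefore remove it.

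Two conclusions are exposed. The first is the primary comparison of traction with no treatment, where an after-effect would be credited as restored length. The second is whether continued use holds the gain better than stopping. At month 6 Group 3 may have used the device recently, while Group 1 has been off it for about three months. In the same way, part of any fall in Group 1 between months 3 and 6 could be the loss of temporary stretch and not regression of a lasting gain. A larger sample would reduce neither problem.

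**Working it through.** **Figures in the plan.** The plan gives no standard deviation, effect size, alpha or power. The only figure to reproduce is the sample size, 4 x 30 = 120 (3.4), which this point does not affect.

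**Step 1: possible recent use at each reading, from 3.5 and 3.6.**

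| Visit | Group 1 | Group 2 | Group 3 | Group 4 |
|---|---|---|---|---|
| Baseline | none | none | none | none |
| Month 3 | twice-daily phase, same-day session possible | as Group 1 | as Group 1 | none |
| Month 6 | about 3 months off | weekly; last session up to about 7 days before if adherent | twice daily for 6 months; same-day session possible if use continues to the visit | none |

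Time since last use is therefore tied to group at both follow-up visits. No section sets it, has it recorded at the visit, or analyses it.

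**Step 2: size under assumed inputs.** Let *a* be the mean after-effect among men with a same-day session, and *p* the share of men who have one. The plan gives neither. Assume *a* = 0.3 to 1.0 cm and *p* = 25% to 75%.

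Month 3, traction against control: inflation = *p* x *a*.
- Low: 0.25 x 0.3 = 0.075 cm
- High: 0.75 x 1.0 = 0.75 cm

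Month 6, Group 3 against Group 1: inflation = *q* x *p* x *a*, where *q* is the share of Group 3 still using the device up to the visit. The protocol does not settle *q*. If it is 1 and *p* is unchanged, the range is the same as at month 3. If it is less than 1, the range is proportionately smaller.

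**Step 3: what such a shift would do to a test.** Assume two-sided alpha 0.05, a normal approximation, all men evaluable and no lasting effect. Let *d* be the mean shift across the group, in SDs of length change. Then SE = sqrt(1/n1 + 1/n2), and the chance of a significant result favouring the group using the device is Phi(*d*/SE - 1.96).

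- Group 3 v Group 1, 30 v 30: SE = sqrt(2/30) = 0.258
- Groups 1 to 3 v Group 4, 90 v 30: SE = sqrt(1/90 + 1/30) = 0.211

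| *d* (SD) | 30 v 30, month 6 | 90 v 30, month 3 |
|---|---|---|
| 0 | 2.5% | 2.5% |
| 0.1 | 5.8% | 6.9% |
| 0.2 | 11.8% | 15.6% |
| 0.3 | 21.2% | 29.6% |
| 0.5 | 49.1% | 66.0% |

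In centimetres the answer depends on an SD that the plan does not give. For a mean shift of 0.25 cm (for example 0.5 cm in half the men), the chance of a significant result in either direction, against a nominal 5%, is:

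| Assumed SD | 30 v 30 | 90 v 30 |
|---|---|---|
| 0.5 cm | 49% | 66% |
| 1.0 cm | 16% | 22% |
| 1.5 cm | 10% | 12% |

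**The case against.** **The mechanism is not in the documents.** No section says that a 30-minute session leaves measurable lengthening, or for how long. Section 1.3 reports how quickly adverse symptoms resolved, but nothing about length. This stands. A reader might infer that the follow-up readings are inflated, but the documents support only that they could be.

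**Group 3 may not be on the device at month 6.** A reader might infer that Group 3 is always measured on a day of use. The objective speaks of length after completion of therapy, the course is six months, and the visit may fall up to 1.5 months later. Some men could have finished well before the reading. This stands, and it weakens the month-6 part. Month 3 is firmer, because the regimen changes only after those assessments.

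**The follow-up reading is not called a stretched length.** Sections 3.6 and 5.2 use stretched length at baseline, but 4.4 does not use the word and the Study Summary refers to total length. Follow-up readings are only apparently stretched.

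**The design already contains a clean comparison.** A reader might infer that the trial cannot show a lasting gain at all. That goes too far. Group 1 against Group 4 at month 6 sets men about three months off the device against untreated men, and is largely free of the problem. Section 5.2, however, does not single it out and refers only to traction against no traction.

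**The journal may show when the device was last used.** It may, although the form is not in the supplied text. It could at best identify affected readings afterwards. It would not prevent them, and no planned analysis uses it.

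**Conclusion.** The gap is real and bears on the primary comparison. Section 4.4 places no condition on time since last use, and the design makes that time differ by group. At month 3 any after-effect would fall wholly on the traction side. At month 6 it could favour Group 3, and less often Group 2, over Group 1, to an extent that depends on whether use continues through the visit window.

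It is a risk of bias, not a shown bias. The range of about 0.08 to 0.75 cm at month 3 rests entirely on assumed values for the after-effect and for the share of men with a same-day session. The Group 3 against Group 1 figure could be smaller. The false-positive rates also assume an alpha and, for the centimetre figures, an SD. They show that a modest shift would matter with 30 men per group, not that one is present. The change is worth making because it is cheap and because a reading taken too soon after a session cannot be corrected later.

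**What to change.** Add to 4.4, as a measurement condition that leaves the assigned amount of use unchanged: at the month-3 and month-6 visits, length is read before any device session that day and before the device-usage review. State this in the visit instructions. Record the date and time of last use on the length form.

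In 5.2:
- Keep all randomised men in the main comparison, whatever their time since last use.
- Report time since last use by group and visit.
- Present Group 1 against Group 4 at month 6 as the comparison for lasting gain.
- Treat any analysis that leaves out readings taken after a same-day session as descriptive only. It would remove men from the device groups alone, selected on behaviour after randomisation.

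Section 3.5 should also say whether use continues through the 1.5-month window. The same-day condition does not address a session the evening before. If the investigators want a longer device-free interval, they should justify its length.

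The cost is one line in the appointment letter, one field on the form, and possibly a smaller observed effect.

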#### 4.5 Schedule of Events

**Table 1: Schedule of Events**

Study Activity	Baseline Assessment	3 Month	6 Month
Consent	X		
IIEF-15	X	X	X
Disease Specific History	X		
Length Assessment	X	X	X
Patient Diary Provided	X	X	
Questionnaire 3 Month		X	
Questionnaire 6 Month			X

### 5 Statistical Plan

#### 5.1 Data Handling

All data will be recorded either by the patient themselves or by the provider directly onto printed forms (Attachments). Information will remain de-identified throughout the remainder of the study period and will remain on password protected, Mayo servers.

After completion of the study, de-identified information will be shared with individuals associated with PathRight Medical, Inc. who may assist with portions of the data analysis and/or manuscript drafting. No identifiable information will be sent.

